6.4.1 Immunogenicity Assessments

For Phase 1/2, there will be two types of humoral immunogenicity assessments:

- Anti-HA antibodies against vaccine-matched strains as measured by HAI or MN assays for primary and secondary analysis.
- Anti-HA antibodies against vaccine-mismatched or drifted strains as measured by HAI or MN assays for exploratory analysis.

For Phase 2 NH and Phase 2 Extension, there will be two types of humoral immunogenicity assessments:

- Anti-HA antibodies against vaccine-matched strains as measured by HAI assay for primary and secondary analysis.
- Anti-HA antibodies against vaccine-matched or vaccine-mismatched strains as measured by HAI, MN assays (or alternative methods) for exploratory analysis.

6.4.2 Phase 1/2

6.4.2.1 Primary Analysis of Immunogenicity Endpoints

For each vaccination group, the following evaluations will be performed at Day 29.

- GMT of vaccine-matched strain-specific anti-HA antibodies with corresponding 95% CI will be provided at Day 29. The following descriptive statistics will also be provided at Day 29: the number of participants (n), median, min, and max.
- GMFR of vaccine-matched strain-specific anti-HA antibodies with corresponding 95% CI will be provided at Day 29 over pre-injection baseline at Day 1. The following descriptive statistics will also be provided at Day 29: the number of participants (n), median, min, and max.
- Proportion of participants with seroconversion (defined as a Day 29 titer $\geq 1:40$ if baseline is $< 1:10$ or a 4-fold or greater rise if baseline is $\geq 1:10$ in anti-HA antibodies measured by HAI assay) will be tabulated with 2-sided 95% Clopper Pearson CIs.

6.4.2.2 Secondary Analysis of Immunogenicity Endpoints

For each vaccination group, the following evaluations will be performed at all evaluable humoral immunogenicity time points (unless otherwise specified).

- GMT of vaccine-matched strain-specific anti-HA antibodies with corresponding 95% CI will be provided at each time point. GM level and corresponding 95% CI will be plotted at each time point. The following descriptive statistics will also be provided at each time point: the number of participants (n), median, min, and max.
- GMFR of vaccine-matched strain-specific anti-HA antibodies with corresponding 95% CI will be provided at each post-baseline time point over pre-injection baseline at Day 1. GMFR and corresponding 95% CI will be plotted at each time point. The following descriptive statistics will also be provided at each time point: the number of participants (n), median, min, and max.
- Proportion of participants with seroconversion at each visit following Day 29. Summaries will be tabulated with 2-sided 95% Clopper Pearson CIs.

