All participants in the Phase 1/2 part of the study will provide a blood specimen before injection on Day 1 and additional blood specimens through the next 6 months for immunogenicity (on Days 8, 29, and 181/EoS). In the Phase 2 NH and Phase 2 Extension parts, all participants will provide a blood specimen for immunogenicity assessments before injection on Day 1 and then on Day 29. In addition, blood samples from a subset of participants at Days 91 and 181/EoS may be used for additional assessments. The Phase 2 Extension part also contains an optional study site visit on Day 4 for blood sample collection for potential biomarker analysis. Furthermore, blood

samples for safety or other medical concerns may be collected according to the Investigator's judgment at scheduled study site visits during each part of the study.

Participants may experience AEs that necessitate an unscheduled visit. There may also be situations in which the Investigator asks a participant to report for an unscheduled visit following the report of an AE. Additional examinations may be conducted at these visits as necessary to ensure the safety and well-being of participants during the study. Electronic case report forms (eCRFs) should be completed for each unscheduled visit.

The study will be observer-blind as to which investigational product (IP; mRNA-1010 or placebo in the Phase 1/2 part; mRNA-1010 or the active comparator in the Phase 2 NH and Phase 2 Extension parts) or dose level is administered. Participants will receive the IP by 0.5-mL IM injection on Day 1. All participants, study site staff involved in participant assessment, and Sponsor personnel (or its designees) will be blinded to individual dosing assignment until the study database is locked and unblinded. Details regarding blinding are provided in [Section 9.1](#) and the study Data Blinding Plan. Preparation of IP for administration will be conducted on site by an unblinded staff member who has no role in the observation or assessment of study participants.

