Immunizations for the Phase 1/2 part of the study are planned during the NH summer and all participants will be recommended to receive a licensed 2021-2022 NH seasonal influenza vaccine during their participation in the study after completion of the Day 29 Visit. Immunizations for the Phase 2 NH part of the study are planned during the NH influenza season. Immunizations for the Phase 2 Extension part are planned during the NH spring.

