4.2. Scientific Rationale for Study Design

This study is designed as an observer-blind study. In the Phase 1/2 part of the study, participants in Vaccination Groups 1 to 3 will receive mRNA-1010 vaccine and those in Vaccination Group 4 will receive placebo. The placebo will be used for descriptive comparisons of safety and immunogenicity. In the Phase 2 NH part, participants in Vaccination Groups 1 to 3 will receive mRNA-1010 vaccine and those in Vaccination Group 4 will receive a licensed quadrivalent seasonal influenza vaccine in order to assess noninferior immunogenicity. In the Phase 2 Extension part, participants in Vaccination Groups 1 to 3 will receive mRNA-1010 vaccine and those in Vaccination Group 4 will receive a licensed quadrivalent seasonal influenza vaccine in order to compare immunogenicity.

In this observer-blind study, all participants, study site staff involved in participant assessment, and Sponsor personnel (or its designees) will be blinded to participant vaccine allocation. A limited number of Sponsor and/or CRO personnel will be unblinded to conduct safety data analyses for the DSMB safety data reviews (as described in the DSMB charter) and perform the IA. Unblinded study personnel, who will not participate in any other aspect of the study, will perform IP accountability, dose preparation, and IP administration.

In the Phase 1/2 part, all participants will provide NP swab samples before the injection on Day 1 for assessment of asymptomatic infection with respiratory pathogens, including influenza virus and SARS-CoV-2, as influenza or COVID-19 symptoms may confound reactogenicity assessments. Furthermore, if a participant experiences an MAAE or any signs or symptoms suggesting ILI and/or COVID-19, an additional NP swab sample will be collected to confirm the diagnosis via RT-PCR. In the Phase 2 NH and Phase 2 Extension parts, the NP swab samples for assessment of infection with respiratory pathogens, including influenza virus and SARS-CoV-2, will be collected anytime from Day 1 through Day 181/EoS if the participants have protocol-defined ILI (Phase 2 NH) or CDC-defined ILI (Phase 2 Extension) or symptoms

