5.3. Lifestyle Restrictions

Participants must not eat or drink anything hot or cold within 10 minutes before oral temperature is taken. Participants in the study should defer vaccination with licensed seasonal influenza vaccine until after completion of their Day 29 Visit, if seasonal influenza vaccine is available and they choose to receive it.

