9.5.3. Immunogenicity Analyses

Immunogenicity analyses in each part of the study will be reported based on the PP Set and provided by vaccination group, unless otherwise specified.

Phase 1/2

For the immunogenicity endpoints, geometric mean of specific antibody titers with corresponding 95% CI at each time point and geometric mean fold rise (GMFR) of specific antibody titers with corresponding 95% CI at each postbaseline time point over preinjection baseline at Day 1 will be provided by vaccination group. The 95% CIs will be calculated based on the t-distribution of the log 2-transformed values and then back transformed to the original scale. Descriptive summary statistics, including median, minimum, and maximum, will also be provided.

For calculation of geometric mean titers (GMTs), antibody titers reported as below the lower limit of quantification (LLOQ) will be replaced by $0.5 \times \text{LLOQ}$. Values that are greater than the upper limit of quantification (ULOQ) will be converted to the ULOQ.

Seroconversion rate from baseline will be provided with a 2-sided 95% CI using the Clopper-Pearson method at each postbaseline time point. Rate of seroconversion is defined as the proportion of participants with either a prevaccination HAI titer $< 1:10$ and a postvaccination HAI titer $\geq 1:40$ or a prevaccination HAI titer $\geq 1:10$ and a minimum 4-fold rise in postvaccination HAI antibody titer.

Further details will be described in the SAP.

Phase 2 Northern Hemisphere

Immune responses, as measured by GMT and seroconversion rate in the mRNA-1010 groups based on Day 29 HAI titers, will be compared with that of participants receiving active comparator for all 4 strains.

An analysis of covariance model will be carried out with HAI titers at Day 29 as a dependent variable and a group variable as the fixed variable. The GMT of the mRNA-1010 at Day 29 will be estimated by the geometric least square mean (GLSM) from the model. The geometric mean ratio (GMTr; ratio of GMT) will be estimated by the ratio of GLSM from the model. The corresponding 2-sided 95% CI will be provided to assess the difference in immune response between the mRNA-1010 compared with the active comparator at Day 29.

The number and percentage of participants with seroconversion due to vaccination will be provided with 2-sided 95% CI using the Clopper-Pearson method at Day 29. The seroconversion rate difference with 95% CI at Day 29 will be provided.

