3.1.2 Secondary Endpoints

The secondary objective will be evaluated by the following endpoints:

- GMT and GMFR of anti-HA antibodies as measured by HAI or microneutralization (MN) assays at all evaluable humoral immunogenicity time points compared with Day 1 (baseline).

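### Phase 1/2 Day 181 titers are summarised by group without separating those drawn after the licensed influenza vaccine recommended to everyone after Day 29

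*SAP*

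**What the plan says.** **The later vaccine.** Protocol 4.1 plans Phase 1/2 immunisation for the Northern Hemisphere summer and says "all participants will be recommended to receive a licensed 2021-2022 NH seasonal influenza vaccine during their participation in the study", once the Day 29 Visit is done. Protocol 5.3 leaves receipt to the participant: "if seasonal influenza vaccine is available and they choose to receive it".

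**Sampling.** Phase 1/2 postbaseline humoral samples are taken "on Days 8, 29, and 181/EoS" (Protocol 4.1).

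**Analysis.** SAP 6.4.2.2, by vaccination group: "GMT of vaccine-matched strain-specific anti-HA antibodies with corresponding 95% CI will be provided at each time point". GMFR is given at each postbaseline time point, and both are plotted. It also lists "Proportion of participants with seroconversion at each visit following Day 29". Protocol 9.5.3 says of Phase 1/2: "Seroconversion rate from baseline will be provided with a 2-sided 95% CI using the Clopper-Pearson method at each postbaseline time point". SAP 3.1.2 makes GMT and GMFR at all evaluable time points the Phase 1/2 secondary endpoints. Day 181 seroconversion is a planned analysis but not a listed endpoint. On the control arm, Protocol 4.2 says: "The placebo will be used for descriptive comparisons of safety and immunogenicity".

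**Other vaccines.** The criterion in Protocol 6.5.3 on licensed vaccines, which can remove a participant from the Per-Protocol Set, covers the 28 days after study vaccination. SAP 6.2.4 counts seasonal influenza vaccine by group over the same 28 days and puts non-study vaccinations otherwise in a listing. Footnote 11 of SAP 9.5.1 has non-study vaccinations recorded for 28 days; Protocol Table 1 (footnote 11) and Protocol 6.5.2 record them through Day 181/EoS.

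**The concern.** A group's Day 181 value is naturally read as what remains of the study vaccine's effect, set against placebo. If an unknown share of each group has had another influenza vaccine in between, the value describes neither mRNA-1010 nor placebo alone. The placebo arm is the clearest case: a rise over baseline, or a seroconversion, at Day 181 could come entirely from the licensed vaccine. With no count by group, the reader of the tables cannot judge how much of the result is affected.

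**Working it through.** **Step 1: can an existing rule catch these titers?**

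| Possible safeguard | Where | Reach |
|---|---|---|
| Licensed-vaccine criterion | Protocol 6.5.3 | 28 days after study vaccination |
| Influenza-infection clause | SAP 5.3 | Baseline through Day 29; infection only |
| Major-deviation clause | SAP 5.3 | Would not apply: the protocol itself recommends the vaccine |
| Day 181 window for unscheduled samples | SAP Appendix B, Table 3 | Study day 106 onward; no condition on other vaccines |
| Phase 1/2 subgroups | SAP 6.1.1 | Age only |
| Restriction to evaluable time points | SAP 6.4.2.2 | Term undefined; excludes no titer |
| Seasonal-vaccine count | SAP 6.2.4 | Day of injection plus 27 days |

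None does. The count closes just before the recommended vaccination would normally begin. The exception is a Day 29 Visit held early within its ±2-day window, which is negligible.

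**Step 2: could the licensed vaccine raise these titers?** Its composition is not given. Protocol 4.1 lists the strains for 2021-2022 NH cell- or recombinant-based vaccines, and three of the four match the Phase 1/2 strains; only H3N2 differs. Some effect on vaccine-matched titers is plausible.

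**Step 3: inputs.** The plan has no figure for Day 181. Its only Phase 1/2 sample-size figures are the chances of seeing at least one AE with n = 45 (Protocol 9.3). They reproduce: 1 − 0.95^45 = 0.9006 and 1 − 0.90^45 = 0.9913. Group size is therefore taken as 45. Uptake p and the remaining fold rise F at Day 181 are assumptions throughout.

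**Step 4: inflation of a group's Day 181 GMT or GMFR.** If a share p keeps a fold rise F, the geometric mean is multiplied by F^p.
- p = 0.3, F = 2: 2^0.3 = 1.23
- p = 0.5, F = 3: 3^0.5 = 1.73
- p = 0.7, F = 4: 4^0.7 = 2.64, combining both upper assumptions

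**Step 5: between-group ratios.** With equal p and F in two arms, the ratio is unchanged.
- *Unequal uptake.* A 20-point difference shifts the ratio by F^0.2: 1.15 (F = 2), 1.25 (F = 3), 1.32 (F = 4).
- *How likely by chance.* With equal true uptake, the SD of the difference between two arms is √(2p(1 − p)/45), which is 9.7 points at p = 0.3 or 0.7 and 10.5 at p = 0.5. A difference of at least 20 points (9 of 45) between two given arms has two-sided probability 3.8% and 5.8% (normal), or 5.0% and 7.3% (exact binomial). For at least one of the three mRNA-1010 groups against placebo, it is about 13% to 18%.
- *Unequal rise.* With equal uptake, the ratio is multiplied by (F_mRNA/F_placebo)^p. With 50% uptake, a 4-fold rise on placebo and 2-fold on mRNA-1010, a true ratio of 2 would appear as 2 × (2/4)^0.5 = 1.41.

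**Step 6: what is left after excluding affected titers.** Remaining n = 45(1 − p), rounded down. The log-scale CI half-width at equal SD is proportional to t(0.975, n − 1)/√n; for n = 45 this is 2.015/√45 = 0.300.

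| Uptake | n | t | t/√n | Width relative to n = 45 |
|---|---|---|---|---|
| 30% | 31 | 2.042 | 0.367 | 1.22 |
| 50% | 22 | 2.080 | 0.443 | 1.48 |
| 70% | 13 | 2.179 | 0.604 | 2.01 |

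**The case against.** Phase 1/2 is descriptive, tests no hypothesis and has its primary immunogenicity results at Day 29. Persistence is not a stated Phase 1/2 objective. An all-data summary by assigned group, under a protocol that recommends the later vaccine to every arm, is a legitimate description of what happens under that policy. Listings would let a reader trace individual cases. The restricted summary is small, and its members select themselves after randomisation. On this view, a count and a footnote would suffice.

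Much of this is fair. It is why the all-data summary should stay and why the matter does not touch the primary conclusions. It does not remove the gap: the plan neither states that it intends such a policy reading nor gives the count needed to interpret it, and listings do not correct a group GMT, a plotted curve or a placebo seroconversion rate.

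Two narrower points stand as cautions. The remaining sample sizes start from 45 randomised, so they are upper limits at each assumed uptake; the Per-Protocol Set with a Day 181 sample will be smaller. Also, the amendment history (Protocol 11.5) dates the specification to record non-study vaccinations throughout the study to Amendment 3, after the Phase 1/2 interim results. The current text requires those records, but how complete the dates are for earlier vaccinations should be checked.

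**Conclusion.** The concern holds. Followed as written, the plan gives Phase 1/2 Day 181 GMT, GMFR and seroconversion by group with an uncounted contribution from a licensed influenza vaccine. It affects secondary endpoints and one further planned analysis. Day 29 is unaffected, and no Phase 1/2 contrast is formally estimated.

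The true size is unknown. Under assumed uptake of 30% to 70% and a remaining 2- to 4-fold rise, placebo Day 181 GMT would be about 1.2 to 2.6 times too high as a placebo value. Between-group ratios would move less if uptake and rise are similar across arms, which the blind makes more likely for uptake than for rise. This should be fixed: the remedy is cheap, and without it the group-level Day 181 results cannot be read as effects of the assigned product.

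**What to change.** 1. **SAP 6.4.2.2 (Phase 1/2 only).** Flag every Day 181 titer collected after a non-study influenza vaccination. Present Day 181 GMT, GMFR and seroconversion with flagged titers excluded, beside the all-data summary. State that the denominator of the restricted summary is participants with an evaluable baseline titer and an unflagged evaluable Day 181 titer, so that flagged participants are not counted as non-responders.
2. **SAP 6.2.4.** Tabulate by vaccination group the number and percentage receiving a non-study influenza vaccine from after the Day 29 Visit through Day 181.
3. **SAP 9.5.1, footnote 11.** Align it with Protocol Table 1 and 6.5.2, which record non-study vaccinations through Day 181/EoS; the flag depends on those dates.

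The cost is SAP wording, one derived flag, one extra summary and one count, using dates the protocol already requires. The restricted summary will be less precise, with CIs roughly 1.2 to 2.0 times wider under the assumed uptake, and rests on a subset self-selected after randomisation. Neither summary is sufficient alone, so both should be shown.

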6.4.2.3 Exploratory Analysis of Immunogenicity

The below exploratory analyses of immunogenicity may be performed:

- GMT of vaccine-mismatched strain-specific anti-HA antibodies with corresponding 95% CI will be provided at each time point using methods described in [Section 6.4](#).
- GMFR of vaccine-mismatched strain-specific anti-HA antibodies with corresponding 95% CI will be provided at each post-baseline time point over pre-injection baseline at Day 1 using methods described in [Section 6.4](#).
- Descriptive summaries of virus-specific T-cell and B-cell responses measured by flow cytometry or other methods as well as targeted repertoire analysis of B cells and T cells after vaccination.
- Descriptive summaries of immunologic endpoints to further characterize antibody responses.
- The number of participants with confirmed influenza infection by RT-PCR test.
- Listing of immune response of participants infected by influenza

6.4.3 Phase 2 Northern Hemisphere and Phase 2 Extension

6.4.3.1 Primary Analysis of Immunogenicity Endpoints

Immune responses, as measured by GMT and seroconversion rate in the mRNA-1010 groups based on Day 29 anti-HA antibodies titers as measured by HAI assay, will be compared with that of participants receiving active comparator for all 4 strains.

For Phase 2 NH and Phase 2 Extension, the following evaluations will be performed at Day 29:

- An analysis of covariance (ANCOVA) model will be carried out with anti-HA antibodies titers at Day 29 as a dependent variable and vaccination group as an independent variable. This model will be adjusted for the baseline antibody titer. For Phase 2 NH, age group and vaccination status will be included as covariates. For Phase 2 Extension, age group will be included as a covariate. The GMT of vaccine-matched influenza A and B strains at Day 29 will be estimated by the geometric least square mean (GLSM) from the model (model-based GMT). The ratio of GMT (GMTr) will be estimated by the ratio of GLSM from the model. The corresponding 2 sided 95% CI will be provided to assess the difference in immune response between the mRNA 1010 compared with the active comparator at Day 29. The model will be conducted based on the log transformed values then back transformed to the original scale for presentation.
- The number and proportion of participants with seroconversion (defined in [Section 3.2.1](#)) at Day 29 will be provided with 2-sided 95% CI using Clopper Pearson method for each vaccination group. To compare the seroconversion rates between the vaccination groups, the Miettinen-Nurminen's method will be used to calculate the 95% CI for the difference in the seroconversion rates.

The analyses above may also be performed by vaccination status.

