6.5.2. Concomitant Medications and Therapies

At each study visit, study site staff must question the participant regarding any medications taken and nonstudy vaccinations received by the participant and record the following information in the eCRF:

- All nonstudy vaccinations administered within the period starting 28 days before the IP injection and through Day 181/EoS.
- Any seasonal influenza vaccine administered since September 2020 (Phase 2 NH) or since September 2021 (Phase 2 Extension).
- Any authorized or investigational COVID-19 vaccine at any time before the IP injection and through Day 181/EoS.
- All concomitant medications taken through 28 days after the IP injection. Antipyretics and analgesics taken prophylactically (ie, taken in the absence of any symptoms in anticipation of an injection reaction) will be recorded as such.
- Systemic steroids (≥ 10 mg/day of prednisone or equivalent), immunosuppressants, immune-modifying drugs, immunoglobulins, and/or blood products administered at any time during the study period after the IP injection.
- Any concomitant medications relevant to or for the treatment of an SAE, AESI, or an MAAE from Day 1 through Day 181/EoS.
- The participant will be asked in the eDiary if they have taken any antipyretic or analgesic to treat or prevent fever or pain within 7 days after the study vaccination, including the day of injection. Reported antipyretic or analgesic medications should be recorded in the source document by the study site staff during the study visits after vaccination or via other participant interactions (eg, telephone calls).

Concomitant medications (including vaccinations) will be coded using the WHODrug Global.

If a participant takes a prohibited drug therapy, the Investigator and the CRO's medical monitor will make a joint decision about continuing or withholding the study vaccination of the participant based on the time the medication was administered, the drug's pharmacology and pharmacokinetics, and whether use of the medication will compromise the participant's safety or interpretation of the data. It is the Investigator's responsibility to ensure that details regarding the concomitant medications are adequately recorded in the eCRF.

6.5.3. Concomitant Medications and Vaccines That May Lead to the Elimination of a Participant From Per-Protocol Analyses

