4.2 Statistical Hypotheses

No formal hypotheses will be tested for Phase 1/2, Phase 2 NH, and Phase 2 Extension.

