4.3.3 Phase 2 Extension

Approximately 200 participants will be randomly assigned in a 1:1:1:1 ratio to the mRNA-1010 6.25, 12.5, 25 µg groups, or the active comparator Group. A total of 150 participants will receive the mRNA-1010 vaccine (50 participants at each dose level). With 50 participants receiving an investigational vaccine, there is a probability of approximately 92% to observe at least 1 participant with an AE, if the true incidence rate of the AE is 5%; if the true incidence rate is 10%, then the probability to observe it will be approximately 99%.

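### The Phase 2 Extension ANCOVA could adjust for seasonal influenza vaccine received since September 2021, which is already recorded; the gain is small and the cost is one model term

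*SAP*

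**What the plan says.** SAP 6.4.3.1 specifies one ANCOVA for log-transformed Day 29 HAI titer in both Phase 2 parts, with vaccination group as the factor of interest. For both, "This model will be adjusted for the baseline antibody titer". The other covariates differ by part: "For Phase 2 NH, age group and vaccination status will be included as covariates", whereas "For Phase 2 Extension, age group will be included as a covariate". The output is the GMT ratio of each mRNA-1010 dose to the active comparator: "The corresponding 2 sided 95% CI will be provided to assess the difference in immune response".

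The categorical covariates match each part's randomization. NH is stratified by age (three levels) and previous-season vaccination (SAP 4.4.2). The Extension is stratified by age only, in two levels (SAP 4.4.3).

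On data collection, Protocol 6.5.2 requires sites to record "Any seasonal influenza vaccine administered since September 2020 (Phase 2 NH) or since September 2021 (Phase 2 Extension"). Protocol 5.2.3 excludes from the Extension anyone given an influenza vaccine within 180 days before the randomization visit. Protocol 4.1 plans Extension dosing for the Northern Hemisphere spring.

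SAP 6.1.2 defines vaccination-status groups for NH; SAP 6.1.3 defines none for the Extension. Yet SAP 6.4.3.1, whose parent heading covers both parts, allows the primary analyses to be repeated by vaccination status without saying to which part that applies.

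**The concern.** A recent influenza vaccination can affect both the titer a participant starts with and the response to the next dose. Baseline titer captures part of this, but the NH model contains baseline titer and still carries a vaccination-status term. In the Extension, with about 50 per arm and no stratification on this factor, the arms can differ by chance in the share recently vaccinated, and the model has no term for it. One comparator arm serves all three dose contrasts and all four strains, so an imbalance there would affect every GMT ratio in the part.

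What is at stake is some conditional accuracy and a little precision in the primary immunogenicity estimates of the Extension. No test or decision rule depends on it: "No formal hypotheses will be tested for Phase 1/2, Phase 2 NH, and Phase 2 Extension".

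**Working it through.** **The plan's own figure.** The Extension has no stated precision or power for the GMT ratio. Its only sample-size figure is for adverse events: with 50 per dose group, "there is a probability of approximately 92% to observe at least 1 participant with an AE" at a 5% true rate. Check: 1 - 0.95^50 = 0.923, which agrees. At a 10% rate, 1 - 0.90^50 = 0.995, against a stated approximate 99%.

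**Inputs from the documents.** "Approximately 200 participants will be randomly assigned in a 1:1:1:1 ratio to the mRNA-1010 6.25, 12.5, 25 µg groups, or the active comparator Group" (SAP 4.3.3), so 50 per arm; two-sided 95% intervals; covariates as above.

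**Assumed inputs, since the documents give none of them.** Share previously vaccinated, p: 10-50%. Residual SD of log2 titer given the modelled covariates: 1.2-2.0. Residual effect of prior vaccination given baseline titer and age: 0 to 1.0 log2, with 1.5-fold (log2 1.5 = 0.585) for illustration.

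**1. Can the variable be built?** The year 2022 is inferred from the date of Amendment 4, 3 February 2022 (SAP Section 1). A participant randomized on 20 March 2022 is eligible only if last vaccinated before about 21 September 2021; for 20 June 2022 the cut-off is about 22 December 2021. Counting from 1 September, the window that is both recorded and eligible is about 20 to 112 days. The variable exists, but fewer people will have it than in an unrestricted population, so p should be taken as low as 10%.

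**2. Chance imbalance in one contrast.** The SD of the difference in shares is sqrt(2p(1-p)/50): 0.060, 0.092 and 0.100 at p = 10%, 30% and 50%. The exact binomial probability of a difference of at least 10 points is 13%, 33% and 37%; of at least 20 points, 0.2%, 3.8% and 5.7%.

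**3. Chance imbalance in any of the three contrasts.** Condition on the comparator count c, cube the probability that a dose arm lies within 4 participants of c, and average over c. The chance that at least one contrast is off by 10 points or more is 30%, 64% and about 70% at p = 10%, 30% and 50%.

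**4. Effect on a GMT ratio.** The shift is 1.5 raised to the imbalance:

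| p | one SD | two SD |
|---|---|---|
| 10% | 1.5^0.060 = 1.025 | 1.5^0.120 = 1.050 |
| 30% | 1.5^0.092 = 1.038 | 1.5^0.183 = 1.077 |
| 50% | 1.5^0.100 = 1.041 | 1.5^0.200 = 1.084 |

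**5. Effect on interval width.** Let s be the residual SD with the covariate in the model and d its residual effect in log2. The half-width is t(194) × sqrt(s² + p(1-p)d²) × sqrt(2/50) without the covariate, and t(193) × s × sqrt(2/50) × sqrt(1 + 1/193) with it. Width ratio, with to without:

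| s | p | d = 0 | d = 0.5 | d = 0.585 | d = 1.0 |
|---|---|---|---|---|---|
| 1.5 | 10% | 1.003 | 0.998 | 0.996 | 0.983 |
| 1.5 | 30% | 1.003 | 0.991 | 0.987 | 0.959 |
| 1.5 | 50% | 1.003 | 0.989 | 0.984 | 0.951 |
| 1.2 | 50% | 1.003 | 0.982 | 0.974 | 0.926 |

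The last row is the most favourable corner of the grid. At s = 1.5, p = 30% and d = 0.5, the 95% multiplier on the GMT ratio goes from 1.514 to 1.509.

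**6. Check by simulation.** Four arms of 50 with baseline titer in the model (assumed slope 0.5, s = 1.5) gave standard-error ratios of 1.002 for no residual effect, 0.992 for 0.5 log2 at p = 30%, and 0.955 for 1.0 log2 at p = 50%. With no residual effect, baseline titer alone had already cut the standard error by about 11% (0.339 to 0.301).

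**The case against.** The strongest reply is that nothing is missing. Each part's categorical covariates follow its own stratification factors, baseline titer is added to both, and the Extension model is a coherent application of that pattern. This stands: there is no internal contradiction. Nor do the documents say that the sponsor judged both baseline titer and vaccination status to be necessary in NH. Following the stratification factors is a minimum, though, and does not bar a further prespecified baseline covariate; baseline titer is itself unstratified.

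A second reply is that the Extension does not hold NH's variable. This also stands. History goes back only to September 2021 and is cut short by the 180-day exclusion, so a yes depends partly on enrollment date and a no mixes never-vaccinated people with those vaccinated in 2020-21. The proposed term is a new, coarser covariate. This weakens it as a predictor but does not confound the arm comparison, because it is fixed before randomization.

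Three stronger readings are tempting and are not supported:
- **The GMT ratios are biased.** Randomization keeps them unbiased, and their intervals already allow for chance imbalance. A 4% shift is small beside an interval multiplier of about 1.51 under the assumed SD of 1.5.
- **The precision is free and material.** Baseline titer already carries part of the effect. If there is no residual effect, the interval widens by about 0.3%.
- **The fix would align the 25 µg estimate across the two parts.** The models would still differ in age grouping (three levels against two) and in what vaccination status means.

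**Conclusion.** The point holds as a minor, optional improvement. The Extension model leaves prior influenza vaccination neither stratified nor adjusted for, although a usable form of it is recorded. For residual effects up to 0.5 log2 (1.4-fold), the change in interval width runs from +0.3% to about -2%. At 1.5-fold it reaches -2.6% in the most favourable corner, and at 2-fold -7.5%. The shift removed by adjustment is about 2.5-4% of a GMT ratio for a one-SD imbalance and 5-8% for two SD, if the residual effect is 1.5-fold. The share vaccinated, the residual SD and the residual effect are all assumptions, and the eligibility window suggests that the share may sit toward the low end. The planned analysis without the term remains valid.

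**What to change.** Before unblinding of the Extension, define in SAP 6.1.3 a binary baseline variable: seasonal influenza vaccine received from 1 September 2021 and before Day 1 (yes/no). The Day 1 limit matters because Protocol 6.5.2 asks about vaccines at every visit, and a vaccine given after randomization must not enter the covariate. Add the variable to the Extension ANCOVA in SAP 6.4.3.1 alongside baseline titer and age group. State how unknown status is handled and what is done if nearly everyone falls in one category. If the sponsor prefers to leave the primary model unchanged, a prespecified sensitivity analysis with this term would serve.

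In the same edit, state whether the optional analysis by vaccination status covers the Extension and, if so, that it uses this definition.

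The cost is one model term and one degree of freedom out of about 194. The protocol already requires the data, so no new collection is needed.
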